3.5 Supportive Care

All supportive measures consistent with optimal patient care will be given throughout the study.

Diarrhea, nausea and vomiting have all been reported with GSK2636771. Supportive measures with anti-diarrheals and anti-emetics are recommended per investigator discretion or local institutional guidelines for emergence of treatment related symptoms.

GSK2636771 may enhance anti-platelet activity of agents that are irreversible or that act through platelet purinergic receptors. Any need for starting anti-platelet therapy in a patient enrolled to this arm will have to be evaluated by the subprotocol chair. Although aspirin does not act at the purinergic receptor, caution is recommended when GSK2636771 and aspirin are used concomitantly.

3.6 Duration of Agent-specific treatment

In the absence of treatment delays due to adverse event(s), treatment may continue until one of the following criteria applies::

- Extraordinary Medical Circumstances: If at any time the constraints of this
 protocol are detrimental to the patient's health, protocol treatment should be
 discontinued. In this event submit forms according to the instructions in the
 MATCH Forms Packet.
- Patient withdraws consent.
- Patient experiences unacceptable toxicity.
- Non-protocol therapies are administered.
- Disease progression.

3.7 Duration of Follow-Up

Refer to the MATCH Master Protocol for specifics on the duration of follow-up.

ECOG-ACRIN EAY131-P Version Date: February 6, 2017

Study Parameters Rev. 12/16 4 Rev. 3/17

Therapeutic Parameters for GSK2636771 Treatment 4.1

NOTE: In addition to the study parameters listed in the MATCH Master Protocol, the below parameters must also be

performed for patients receiving GSK2636771 treatment.

NOTE: All assessments required prior to registration to treatment should be done ≤ 4 weeks prior to registration to

Steps 1, 3, 5, 7, excluding the radiologic evaluation and electrocardiogram (ECG).

	Drier to Degistration	Treatr	ment	End of Treatment	Follow Up ^F
Test/Assessment	Prior to Registration to Treatment	Every Cycle, prior to treatment	Every 2 Cycles		
H&P, Weight, Vital signs ^A	Х	X ₁			Х
Performance status	Х	X ₁			Х
CBC w/diff, plts ^B	Х	Xì			Х
Serum chemistry ^B	Х	X _J			Х
Radiologic evaluation ^D	Х		XD		X ^F
β-HCG ^c	Х				
Toxicity Assessment ^G		X		Х	X ^F
Pill Count/Diary ^H		X		Х	
ECG ^K	Х	Χı			
Urinalysis	ΧI	Χι			
Tumor biopsy and blood sample submission for MATCH Master Protocol ^E			Х	Х	

A History and physical, including vital signs and weight at the start of each cycle (up to 3 days before start of new cycle).

B. Albumin, alkaline phosphatase, total bilirubin, bicarbonate, BUN, calcium, creatinine, glucose, phosphorus, potassium, SGOT[AST], SGPT[ALT], sodium, magnesium and serum tumor markers (including LDH, PSA if appropriate). For eligibility purposes, participants with creatinine levels above institutional normal. Cockcroft-Gault will be used to calculate creatinine clearance. CBC w/diff. platelets and serum chemistries should be performed on cycle 1, day 1 (or up to 7 days prior), and at the start of each subsequent cycle (up to 3 days before start of new cycle). CBC with differential will be performed more frequently in patients with grade 4 neutropenia or thrombocytopenia until resolution to ≤ grade 3. CBC and serum chemistries are only required in follow-up until values return to pre-treatment levels or until progressive disease.

^{C.} Blood pregnancy test (women of childbearing potential) required prior to beginning treatment.

D. Disease measurements are repeated every 2 cycles for the first 26 cycles, and every 3 cycles thereafter until PD or start of another MATCH treatment step. The baseline evaluation should be performed as closely as possible to the beginning of treatment and never more than 6 weeks

before registration to treatment step. For multiple myeloma patients, please refer to Section 6.4 of the MATCH Master Protocol for additional information on myeloma response criteria and the required disease assessments. Documentation (radiologic) must be provided for patients removed from study for progressive disease.

- E. Additional blood specimens and/or biopsies are to be submitted from consenting patients per the MATCH Master Protocol. Submit at the following time points, as applicable:
 - Blood specimens are to be submitted at the end of Cycle 2 (prior to start of Cycle 3 treatment). If patient progresses or treatment is discontinued prior to Cycle 3, collect the blood at that time instead. See Section 9.3.2.3 of MATCH Master Protocol. On-treatment kits for blood sample collections will be automatically shipped to sites upon registration to the treatment step.
 - Screening biopsies for additional aMOI assessments after registration to appropriate screening step, if applicable (Step 2 or Step 4).
 - At end of all MATCH study treatments, blood specimens and/or research biopsy after consent and registration to Step 8

Please refer to Section 4 of the MATCH Master Protocol to determine whether the patient proceeds to the next screening step or to follow-up (with a potential end of treatment biopsy for research purposes on Step 8). Samples are to be submitted as outlined in Section 9 of the MATCH Master Protocol. To order Step 2/4 Screening or Step 8 kits, complete the EAY131 Collection and Shipping Kit Order Form (See Appendix XII of the MATCH Master Protocol) and fax to [contact].

- F. Every 3 months if patient is < 2 years from study entry, and every 6 months for year 3. Toxicity assessments and radiologic evaluations are not required to be done during Follow Up if progression has been previously reported; however if an adverse event occurs post treatment that meets the SAE reporting requirements, it still must be reported via CTEP-AERS, even if progression has occurred.
- ^{G.} Site personnel should evaluate for toxicity and discuss treatment compliance with the patient in order to ensure the medication is taken correctly; this evaluation may be conducted by telephone or in person. The Toxicity Assessment is not required prior to Cycle 1, but is required every subsequent cycle.
- H. The pill calendar will be collected at the end of every cycle. The Pill Count/Diary is not required prior to Cycle 1, but is required every subsequent cycle.
- ^{1.} As clinically indicated.
- J. For Cycle 1, if the following tests/assessments occurred within 7 days of Day 1, they do not need to be repeated at this timepoint: H&P, Weight, Vital Signs; Performance Status; CBC w/diff, plts; Serum chemistry; Concomitant Medications.
- K. Within 8 weeks of treatment assignment.

5. Drug Formulation and Procurement

This information has been prepared by the ECOG-ACRIN Pharmacy and Nursing Committees.

Availability

NO STARTER SUPPLIES MAY BE ORDERED. Subjects must be enrolled and assigned to the treatment subprotocol prior to submitting the clinical drug request to PMB.

Drug Ordering: NCI supplied agents may be requested by the Principal Investigator (or their authorized designees) at each participating institution. Pharmaceutical Management Branch (PMB) policy requires that drug be shipped directly to the institution where the patient is to be treated. PMB does not permit the transfer of agents between institutions (unless prior approval from PMB is obtained – see general information) The CTEP-assigned protocol number must be used for ordering all CTEP-supplied investigational agents. The responsible investigator at each participating institution must be registered with CTEP, DCTD through an annual submission of FDA Form 1572 (Statement of Investigator), Curriculum Vitae, Supplemental Investigator Data Form (IDF), and Financial Disclosure Form (FDF). If there are several participating investigators at one institution, CTEP-supplied investigational agents for the study should be ordered under the name of one lead investigator at that institution.

Active CTEP-registered investigators and investigator-designated shipping designees and ordering designees can submit agent requests through the PMB Online Agent Order Processing (OAOP) application (https://eapps-ctep.nci.nih.gov/OAOP/pages/login.jspx). Access to OAOP requires the establishment of a CTEP Identity and Access Management (IAM) account (https://eapps-ctep.nci.nih.gov/iam/) and the maintenance of an "active" account status and a "current" password..

NCI Supplied Agent(s) - General Information

Questions about drug orders, transfers, returns, or accountability should be addressed to the PMB by calling [contact] Monday through Friday between 8:30 AM and 4:30 PM Eastern Time or email [contact] anytime.

Drug Returns: All undispensed drug supplies should be returned to the PMB. When it is necessary to return study drug (e.g., sealed bottles remaining when PMB sends a stock recovery letter), investigators should return the study drug to the PMB using the NCI Return Agent Form available on the NCI home page (http://ctep.cancer.gov).

Drug Accountability: The investigator, or a responsible party designated by the investigator, must maintain a careful record of the receipt, disposition, and return of agent received from the PMB using the NCI Investigational Agent Accountability Record Form for Oral Agents available on the NCI home page (http://ctep.cancer.gov). Maintain separate NCI Investigational Agent Accountability Records for each agent, strength, formulation and ordering investigator.

Investigator Brochure Availability: The current versions of the IBs for PMB-supplied agents will be accessible to site investigators and research staff through the PMB Online Agent Order Processing (OAOP) application. Access to OAOP requires the establishment of a CTEP Identity and Access Management (IAM) account and the maintenance of an "active" account status and a "current" password. Questions about IB access may be directed to the PMB IB coordinator at [contact]

Rev. 12/16

Rev. 3/17

EAY131-P Version Date: February 6, 2017

GSK2636771 (NSC 781258) 5.1

5.1.1 Other Names:

GSK2636771B where B denotes the tris (hydroxymethyl) aminomethane salt

5.1.2 Classification:

Phosphoinositide 3-kinase beta (PI3Kβ) inhibitor

5.1.3 Mode of Action:

GSK2636771 is a potent, orally bioavailable, adenosine triphosphate (ATP) competitive, selective inhibitor of phosphoinositide 3-kinase beta (PI3Kβ).

Rev. 12/16 5.1.4 Storage and Stability:

Storage: Store at room temperature up to 30° C (86° F).

Stability: Shelf life studies are ongoing. If needed, sites may repackage capsules in pharmacy bottles and assign a 30-day expiration date.

If a storage temperature excursion is identified, promptly return GSK2636771 to room temperature and guarantine the supplies. Provide a detailed report of the excursion (including documentation of temperature monitoring and duration of the excursion) to [contact] for determination of suitability.

5.1.5 Dose Specifics:

GSK2636771 will be supplied in 100mg capsules. Starting dose will be 400 mg (4 x 100mg capsules) once daily for 28 days per cycle. Dose reductions will be to 300mg and 200mg.

5.1.6 Preparation:

GlaxoSmithKline supplies and the PMB/CTEP/DCTD distributes GSK2636771 as size 0, opaque pink 100 mg capsules (free acid equivalent). Excipients include microcrystalline cellulose, croscarmellose sodium and sodium stearyl fumarate. The capsule shell contains gelatin, titanium dioxide (E171) and red iron oxide (E172)).

Capsules are packaged in high density polyethylene bottles with induction seal liners and child-resistant caps. Each bottle contains 35 capsules.

5.1.7 Route of Administration:

Oral. Take at least 1 hour before or 2 hours after a meal with 200 mL water (about 7 ounces).

5.1.8 Incompatibilities:

GSK2636711 is highly protein bound (99%) in humans. Use caution in patients who are receiving concomitant medications that are also highly protein-bound.

Rev. 12/16

In vitro studies demonstrate that GSK2636711 is not a substrate for CYP450 enzymes or efflux transporter, P-glycoprotein (P-gp). It is primarily eliminated by acyl glucuronidation via unspecified UGT isozymes. Potent inhibitors and inducers of UGT may alter GSK2636711 exposure.

Studies conducted *in vitro* show that GSK2636711 is not an inhibitor of CYP 450 enzymes or an inhibitor of transporters P-gp, breast cancer resistant protein (BCRP) and OATP1B1 and OATP1B3.

GSK2636771 is a weak *in vitro* inhibitor of OAT1, OAT3 and OCT2; however, the interaction risk appears to be low at clinical concentrations.

In vitro studies show that GSK2636711 does not activate the pregnane X receptor (PXR) and theoretically has a low potential to induce CYP450 isozymes.

5.1.9 Side Effects:

See CAEPR in Section 3.3

5.1.10 Nursing/Patient Implications:

GSK2636771 may enhance antiplatelet activity of agents that are irreversible (aspirin) or that act through platelet purinergic receptors (e.g. clopidogrel, ticlopidine, prasugrel). Avoid concomitant use of GSK2636771 in patients taking these anti-platelet agents or in patients who have a history of congenital platelet function defects.

6. Translational Studies

Please refer to the MATCH Master Protocol for information on the Translational Studies.

7. References

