1.3.4 Efficacy

There are limited data available to assess the clinical activity of GSK2636771. In the FTIH study P3B115717 in patients with PTEN loss as determined by IHC, one subject with mCRPC who received 200 mg GSK2636771 once daily had a partial response (PR) per RECIST. There were 16 subjects (with various solid tumors) with stable disease and 8 subjects (with various solid tumors) who continued treatment for at least 6 months.

Rev. 12/16

Version Date: February 6, 2017

2. Selection of Patients

ECOG-ACRIN Patient No.

Each of the criteria in the checklist that follows must be met, along with the eligibility in the MATCH Master Protocol, in order for a patient to be considered eligible for this study. Use the checklist to confirm a patient's eligibility. For each patient, this checklist must be photocopied, completed and maintained in the patient's chart.

In calculating days of tests and measurements, the day a test or measurement is done is considered Day 0. Therefore, if a test is done on a Monday, the Monday four weeks later would be considered Day 28.

	_				
Patient	Patient's Initials (L, F, M)				
Physician Signature and Date					
NOTE	criteria There excep Sectio study, questi Group	does not allow for the issuance of waivers to any protocol specified a (http://ctep.cancer.gov/protocolDevelopment/policies deviations.htm). fore, all eligibility criteria listed in Section 2 must be met, without tion. The registration of individuals who do not meet all criteria listed in on 2 can result in the participant being censored from the analysis of the and the citation of a major protocol violation during an audit. All ons regarding clarification of eligibility criteria must be directed to the t's Executive Officer ([contact]) or the t's Regulatory Officer ([contact]).			
NOTE	been r	stitutions may use the eligibility checklist as source documentation if it has een reviewed, signed, and dated prior to registration/randomization by the eating physician.			
NOTE	: All pat	tients must have signed the relevant treatment consent form			
2.1 Eligibility Criteria:		Criteria:			
	Patients n	nust meet all of the following eligibility criteria:			
	2.1.1	Patients must fulfill all eligibility criteria outlined in Section 3.1 of MATCH Master Protocol (excluding Section 3.1.6) at the time of registration to treatment step (Step 1, 3, 5, 7).			

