2.1.10 Patients must not have any congenital platelet function defects and cannot be on any of the following anti-platelet drugs: clopidogrel, ticlopidine, prasugrel, that act at platelet purinergic receptors.

2.1.10.1 Any need for starting anti-platelet therapy in a patient enrolled to this arm will have to be evaluated by the subprotocol chair.

OPTIONAL:

Physician Signature

This signature line is provided for use by institutions wishing to use the eligibility checklist as source documentation.

3. GSK2636771 Treatment Plan

Rev. 12/16 3.1 Administration Schedule

GSK2636771 will be administered on an oral, daily, continuous administration schedule. The starting dose of the drug will be 400mg (four 100 mg capsules), once daily, which was deemed the maximum tolerated phase II dose from the company sponsored phase I study.

Each cycle of therapy will be 28 days and there will not be any breaks between dosing cycles. Patients must meet the following criteria in order to proceed with the next cycle of treatment:

- ANC ≥ 1,000/µL
- Platelets ≥ 75,000/µL
- Hemoglobin ≥ 9 g/dL
- Phosphorous, magnesium, potassium, and calcium (corrected for albumin) must either be within normal range for labs or no worse than grade 2.
 Supplementations may be used to keep within these ranges.
- Serum creatinine must be ≤ 1.5 x ULN or 24-hour creatinine clearance of
 ≥ 50 mL/min.

Please refer to Section 3.4 for dose modifications. Within cycle toxicity that meets grade 3 or 4 criteria, will necessitate holding of the drug until the toxicity are improved to grade 1 or baseline, unless otherwise specified in the protocol.

Repeat cycles until progression.

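### Section 5.1.10, read plainly, says to avoid GSK2636771 in patients on aspirin, while Section 3.5 asks only for caution and Section 2.1.10 lets aspirin users enrol

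*Protocol*

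**What the plan says.** Four provisions of the protocol deal with anti-platelet drugs.

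- **Section 2.1.10 (eligibility)** excludes congenital platelet function defects and says that patients "cannot be on any of the following anti-platelet drugs: clopidogrel, ticlopidine, prasugrel, that act at platelet purinergic receptors". Aspirin is not listed.
- **Section 2.1.10.1** adds: "Any need for starting anti-platelet therapy in a patient enrolled to this arm will have to be evaluated by the subprotocol chair". Section 3.5 repeats this rule.
- **Section 3.5 (Supportive Care)** warns: "GSK2636771 may enhance anti-platelet activity of agents that are irreversible or that act through platelet purinergic receptors". It then treats aspirin separately: "Although aspirin does not act at the purinergic receptor, caution is recommended when GSK2636771 and aspirin are used concomitantly".
- **Section 5.1.10 (Nursing/Patient Implications)** gives the same warning with examples: "GSK2636771 may enhance antiplatelet activity of agents that are irreversible (aspirin) or that act through platelet purinergic receptors (e.g. clopidogrel, ticlopidine, prasugrel"). Its next sentence is the instruction: "Avoid concomitant use of GSK2636771 in patients taking these anti-platelet agents or in patients who have a history of congenital platelet function defects".

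Section 5 opens by naming its authors: "This information has been prepared by the ECOG-ACRIN Pharmacy and Nursing Committees".

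**The concern.** Sections 3.5 and 5.1.10 start from the same interaction and the same two groups of agents, but arrive at different actions for aspirin. Caution presupposes that the two drugs may be taken together. Avoidance does not.

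The practical case is a patient already on aspirin at entry. Section 2.1.10 admits that patient, and an investigator working from 3.5 would continue aspirin with care. A pharmacist or nurse working from 5.1.10, which is addressed to nursing staff, could conclude that aspirin should stop or that study drug should be withheld. A safety instruction should give one answer whichever section is opened.

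**Working it through.** No arithmetic is involved beyond a count, so the check is a comparison of the texts.

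**1. What each provision says about aspirin**

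| Section | Aspirin named? | Effect for aspirin |
|---|---|---|
| 2.1.10 | No | Not a bar to enrolment |
| 2.1.10.1 (rule repeated in 3.5) | No | Starting any anti-platelet therapy goes to the subprotocol chair, which on its wording can reach newly started aspirin |
| 3.5, aspirin sentence | Yes | Caution with joint use |
| 5.1.10 | Yes | Avoid, on the plain reading |

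Of the four provisions (2.1.10, 2.1.10.1, 3.5 and 5.1.10), two name aspirin. Those two differ in strength, and none of the four states which prevails.

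**2. What the avoidance sentence refers to.** The word "these" in 5.1.10 points back to the preceding sentence, which names aspirin first and as its only example of an irreversible agent. Limiting the reference to the purinergic agents drops one of the two groups just named, with nothing in the wording to signal it. Section 3.5 separates aspirin expressly, and 5.1.10 has no such separation. Section 5 also uses the weaker term where it wants it: 5.1.8 asks for caution with highly protein-bound co-medication. A reader of Section 5 therefore has no reason to take avoidance to mean caution.

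**3. Whether another rule settles it.** The chair-review rule concerns starting therapy, so it does not reach aspirin already being taken. Section 2 provides a query route, but for questions "regarding clarification of eligibility criteria must be directed to the" group's officers, and the eligibility criterion on this point is not in doubt. Aspirin carried into the study is left with two different instructions.

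**4. Compatibility.** A site that avoids the combination satisfies both 3.5 and 5.1.10, at the price of stopping aspirin or withholding study drug, which 3.5 does not ask for. A site that continues aspirin with caution satisfies 3.5 but not the plain wording of 5.1.10.

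**The case against.** The strongest reply is that the conflict hangs on one pronoun and that context favours the harmless reading. Section 5.1.10 couples its anti-platelet agents with congenital platelet function defects. Section 2.1.10 makes the same coupling, and its three drugs are the same three that 5.1.10 lists as purinergic agents. If 5.1.10 is meant to restate 2.1.10, the avoidance advice covers only those agents and nothing conflicts. In addition, 3.5 holds the only sentence specific to joint use of aspirin, and a specific instruction is usually taken to govern a general one. Avoidance advice may also be read as less than a prohibition.

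Much of this stands. The parallel with 2.1.10 is good evidence of intent and indicates which way to correct the text. It does not change what 5.1.10 says to someone who reads only that section, and the protocol states no rule that the specific sentence governs.

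It also stands that the gap is narrow, since newly started therapy goes to the chair, and that the consequence for patients is a possibility, not something shown. The Master Protocol and the patient drug information handout and wallet card were not available for this review and might settle the matter.

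A reader might go further and infer that the protocol contradicts itself on whether aspirin users are eligible. It does not: 2.1.10 is clear, and 5.1.10 is not an eligibility criterion. A reader might also infer a demonstrated bleeding hazard. The protocol says only that the drug may enhance anti-platelet activity. No bleeding term appears among the adverse events in Section 1.3.2 or in the human-data lists of Section 3.3.

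**Conclusion.** The point holds as a minor inconsistency: the wording of 5.1.10 is wrong as it stands, because it calls for avoidance where 3.5 calls for caution in patients whom 2.1.10 admits. The purinergic-only meaning is probably what was intended, but it is not written.

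The conclusion rests on the plain reading of the pronoun in 5.1.10 and on nothing in the unseen documents giving one section precedence. The number of patients concerned cannot be derived, because the protocol gives no share of patients on aspirin. The consequence is confined to how concomitant aspirin is handled. The documents give no ground for inferring any effect on the endpoints, the accrual goal of 35 or the analysis.

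**What to change.** Replace the second sentence of 5.1.10 at the next addendum so that it says three things:

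- Avoid GSK2636771 in patients on agents acting through platelet purinergic receptors (such as clopidogrel, ticlopidine or prasugrel) and in those with a history of congenital platelet function defects.
- Aspirin already being taken at entry may be continued with caution, with a reference to Section 3.5.
- Any need to start anti-platelet therapy on study, aspirin included, goes to the subprotocol chair, with references to Sections 2.1.10.1 and 3.5.

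The third item matters: a general permission for aspirin with caution would let newly started aspirin bypass the chair review that the protocol already requires. This option changes one passage of 5.1.10 and leaves 2.1.10 and 3.5 as they are. It needs no extra patients, visits or procedures.

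If the sponsor does intend aspirin to be avoided, the aspirin sentence in 3.5 should be changed to say so. Resolving the conflict does not require an enrolment exclusion. If one is wanted, 2.1.10 must be reworded and not merely extended, because its list is defined as drugs acting at purinergic receptors and 3.5 states that aspirin does not act there. Such an exclusion would also remove aspirin users from the eligible population, at a cost to accrual that the protocol does not allow to be estimated.
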